## Study Background

Multiple sclerosis (MS) is a neurological disorder characterized by a wide variety of disabling symptoms including motor and sensory disturbance, cognitive deficits, visual impairment, pain, fatigue and spasticity. Notably, cognitive impairment (CI) occurs in up to 70% of people with MS (Chiaravalloti & DeLuca, 2008) and has a profound influence on a patient's personal functioning, social interaction, employment status and overall quality of life. The most commonly affected cognitive domains are attention, speed of information processing, executive function and memory (Achiron & Barak, 2003; Rogers & Panegyres, 2007), and influence everyday life, from finding an individual's telephone number in the telephone directory to making a plan for a day. Although disease modifying therapies (DMTs) that target primarily the inflammatory immunopathology of MS (Birnbaum, 2010; Lopez-Diego & Weiner, 2008) can slow progression of impairments including CI, existing DMTs are only partially effective or ineffective in *improving* impaired cognition in MS patients (Geisler et al., 1996; Lovera et al., 2010; Shaygannejad, Janghorbani, Ashtari, Zanjani, & Zakizade, 2008). Therefore, it is of utmost importance to develop alternative therapeutic approaches to alleviate CI in MS.

Recently, different forms of non-invasive transcranial electrical stimulation (tES) have been probed as non-pharmacological interventions in several neurological and psychiatric disorders given its safety, portability and potential for at-home application. The two main forms of non-invasive tES are: transcranial **direct** current stimulation (tDCS) and transcranial **alternating** current stimulation (tACS). Preliminary studies have shown promise that tDCS may serve as a tool to ameliorate cognition (Mattioli, Bellomi, Stampatori, Capra, & Miniussi, 2016), pain (Ayache et al., 2016; Mori et al., 2010), fatigue (Ferrucci et al., 2014; Hanken et al., 2016) and sensory deficits (Mori et al., 2013) in patients with MS. For example, Mattioli et al (2016) reported that tDCS over the prefrontal cortex improves attention, information processing speed and executive function (Mattioli et al., 2016). Furthermore, this improvement in cognition was sustained six months after the last treatment. While these studies provide intriguing support for tES as a new therapeutic strategy for MS patients, tES research in MS remains in its infancy and there are no consensus recommendations for its use in MS. Furthermore, the effects of the tACS form of tES on cognitive function in MS patients have not yet, to our knowledge, been assessed.

TACS applies weak sinusoidal currents to the brain through the scalp in a frequency-specific manner and is capable of entraining endogenous brain oscillations and enhancing cognitive function including attention ([name], [name], & [name], 2019; [name], [name], van Schouwenburg, & [name], 2017), working memory (Meiron & Lavidor, 2014; Polania, Nitsche, Korman, Batsikadze, & Paulus, 2012; Vosskuhl, Huster, & Herrmann, 2015), response inhibition (Joundi, Jenkinson, Brittain, Aziz, & Brown, 2012), and fluid intelligence (Pahor & Jausovec, 2014; Santarnecchi et al., 2013). TACS capitalizes on

the fact that a wide range of cognitive capabilities are mediated by the dynamic modulation of rhythmic oscillatory activity, whereas tDCS only applies broad increases or decreases in cortical excitability. Therefore, tACS could provide an advantage over tDCS through a more principled approach by specifically targeting deficient oscillatory neural activity. Importantly, abnormalities in oscillatory brain dynamics have been associated with impaired cognition in MS (Kiiski et al., 2012; Van der Meer et al., 2013). For example, MS patients have significantly reduced theta power in the prefrontal cortex (PFC) compared to both healthy controls and MS patients without CI (Kiiski et al., 2012), indicating theta power reduction in the PFC is a feature of more advanced cognitive impairment in MS. Indeed, PFC theta oscillations are related to information processing tasks, especially those of attention and other executive functions (Gevins, Smith, McEvoy, & Yu, 1997; Klimesch, 1999; Mizuhara, Wang, Kobayashi, & Yamaguchi, 2004). A collective view of these findings leads to the hypothesis that cognitive disturbance in MS may be mitigated by targeting disturbances in oscillatory brain dynamics by applying theta-tACS over the PFC.

[figure not shown]
## Study Objectives

The goals of this proposed study are to 1) evaluate the potential of using frontal theta-tACS during a cognitive task to mitigate cognitive disturbance in MS, specifically, information processing speed and attention, and 2) understand stimulation response variability at the individual-level. Processing speed and attention will be targeted for remediation due to the prevalence of their decline in MS and our previous research (and others) that show tACS may improve these cognitive functions.

## Study Design

**Overall strategy.** We will enroll forty adult MS patients (aged 18-65 years) randomly assigned to one of two groups: either a Verum (6 Hz) tACS group or a Frequency Control (1 Hz) group. Twenty participants in each group will correspond with >80% power ( $1-\beta$ ) at a 95% significance level ( $1-\alpha$ ) as calculated from our preliminary studies. The two groups will be age-matched. A randomized double-blinded, placebo controlled, multi-session

**Fig 1. Structure of the experiments**

experiment is proposed to assess whether tACS may yield improvements in divided attention and information processing speed in MS (Specific Aim 1) and identify predictive factors of response to tACS (Specific Aim 2). The experimental paradigm consists of 5 daily sessions (conducted over up to 10 days) (Fig 1). During session 1 (baseline; pre-tACS) and session 5 (follow-up; post-tACS), participants will be assessed on divided attention while electroencephalography (EEG) data is acquired. EEG data will enable assessments of neuroplastic changes associated with tACS effects on divided attention and it will also serve to quantify cortical excitability as a predictor for tACS effects. Additionally, processing speed will be assessed along with questionnaires on pain and fatigue. During sessions 2-4, tACS will be applied while participants are engaged in a tablet-based multitasking task, which includes divided attention and processing speed components, but is distinct from the primary outcome measures.

**Inclusion/Exclusion Criteria.** Inclusion Criteria: age 18-65, diagnosis of MS (relapsing or progressive) according to McDonald criteria (Polman et al., 2011), Expanded Disability Status Scale (EDSS)≤6.5 (Noseworthy et al., 1990), no paresis of the upper limbs, a minimum of 3 months since the last relapse, no severe depression (Beck Depression Inventory<19), normal hearing, and no changes in MS or symptomatic medications in past 2 months. Exclusion Criteria: prior brain surgery, clips in brain, epilepsy or other neurological or non-affective psychiatric disorders, pregnancy.

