## Protection for Human Subjects

### Risks To The Participants.

**a. Human Participants Involvement and Characteristics:** In this proposal, we will recruit people with MS. General inclusion criteria for all participants are: age 18-65, diagnosis of MS (relapsing or progressive) according to McDonald criteria, Expanded Disability Status Scale (EDSS)  $\leq 6.5$ , no paresis of the upper limbs, a minimum of 3 months since the last relapse, no severe depression (Beck Depression Inventory<19), normal hearing, and no changes in MS or symptomatic medications in past 2 months. Exclusion: prior brain surgery, clips in brain, epilepsy or other neurological or non-affective psychiatric disorders, pregnancy. Because of the difficulties in interpreting cognitive studies in participants with English as a second language, only native-English speakers will be asked to participate in the study. Participants will be selected in an unbiased fashion with regard to sex and race. Gender and minority representation issues do not interact with any of our hypotheses. Therefore, the participants that we recruit will be representative of previous populations studied at University of California, San Francisco and will be represented in the approximate proportions that we have listed. Every effort will be made to ensure that the participant population conforms to the NIH policy on Gender and Minority Inclusion in Research Study populations.

**b. Sources of Materials:** Behavioral and EEG data will be collected from each individual. Information obtained from the studies in the research plan will be strictly confidential, except as required by law, but will be made available to the participant in response to a specific request from the participant. All data will be identified only by a code number. There will be only one "key" linking a participant's name and personal information with their code number. This key, and all participant information and data, is maintained in files in locked cabinets in locked lab space or password protected computer files. Only

the Principal Investigator and research staff has access to these files. Typically, only group averages are reported in scientific communications. Where individual data are reported (e.g., showing example representations of brain activation), individuals are not identified.

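### Entry does not require cognitive impairment and the primary analysis does not adjust for baseline cognition, so a positive result could not separate mitigation of impairment from enhancement of normal cognition

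*Combined protocol and SAP*

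**What the plan says.** - **Aim.** Study Objectives sets out to "evaluate the potential of using frontal theta-tACS during a cognitive task to mitigate cognitive disturbance in MS", naming processing speed and attention as the functions to be remediated.
- **Rationale.** Study Background reports that "MS patients have significantly reduced theta power in the prefrontal cortex (PFC) compared to both healthy controls and MS patients without CI", "indicating theta power reduction in the PFC is a feature of more advanced cognitive impairment in MS". The treatment hypothesis follows from that deficit.
- **Prevalence.** Study Background also states that "cognitive impairment (CI) occurs in up to 70% of people with MS".
- **Entry.** The Inclusion/Exclusion Criteria in Study Design begin "Inclusion Criteria: age 18-65, diagnosis of MS (relapsing or progressive) according to McDonald criteria". They go on to EDSS, arm function and time since relapse, and end with "no severe depression (Beck Depression Inventory<19), normal hearing, and no changes in MS or symptomatic medications in past 2 months". The list under Protection for Human Subjects repeats these and adds that "only native-English speakers will be asked to participate in the study". Neither list has a cognitive test, a cognitive complaint or a theta criterion.
- **Allocation.** "We will enroll forty adult MS patients (aged 18-65 years) randomly assigned to one of two groups"; the groups are to be matched on age. The timing of randomisation relative to session 1 is not given.
- **Primary analysis.** Statistical Design and Power specifies Group and Session as factors for both primary outcomes, with age as the covariate.
- **Aim 2.** The predictors are modelled electric field, evoked potentials, MSFC4, age, gender, education, MS duration and EDSS. Baseline SDMT and baseline d-prime cost are not among them.

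**The concern.** The aim and the mechanism concern impaired cognition, but the sample is MS patients at large. The plan itself expects response to depend on severity. The Aim 2 covariates section says the most severely affected patients benefit most from neurostimulation, and Preliminary Study 2 found SDMT gain associated with clinical severity. Yet the Aim 1 tests make no use of baseline cognitive level beyond its role as the first of two sessions.

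What is at stake is mainly interpretation. If the Group x Session interaction is significant, the planned Aim 1 analysis gives one average effect over impaired and unimpaired patients. It cannot show whether a deficit was reduced or normal performance was raised. A secondary cost is precision: in 40 patients, baseline differences that predict change add noise that could be removed with data already being collected.

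**Working it through.** **1. Share without impairment.** Impairment is put at up to 70%, so the complement is at least 1 - 0.70 = 30%. If enrolment mirrored that bound, this is 0.30 x 40 = 12 patients, or 6 per arm. Sampling alone gives a 95% binomial range of 7 to 18 of 40. The true share in this clinic is not stated and could be lower or higher.

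**2. Where baseline cognition enters the plan.**

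| Stage | Use of baseline cognition |
|---|---|
| Eligibility (both lists) | None |
| Allocation | None; age only |
| Primary analysis | As the pre-tACS level of Session; not as a covariate or moderator |
| Aim 2 | PASAT only, one of four MSFC4 domains |

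**3. Chance imbalance.** With 12 unimpaired among 40 split 20/20, the hypergeometric probability of a split of 8 v 4 or worse, in either direction, is about 30%. A stable difference in level cancels from the Group x Session contrast. It matters only where baseline predicts change or response.

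**4. Gain from adjusting for baseline.** With two sessions, the Group x Session test is a comparison of change scores. For equal variances and pre-post correlation rho:
- variance of change is proportional to 2(1 - rho);
- variance after adjustment for baseline is proportional to 1 - rho^2;
- ratio of standard errors = sqrt((1 + rho)/2).

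The documents do not give rho, so a range is assumed:
- rho = 0.5: sqrt(0.75) = 0.866, standard error 13% smaller;
- rho = 0.65: sqrt(0.825) = 0.908, 9% smaller;
- rho = 0.8: sqrt(0.90) = 0.949, 5% smaller.

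Simulation with 40 patients, which counts the cost of estimating the slope, gives roughly 5-12% over the same range. Stratified allocation alone gives about 5%.

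**5. What a Group x impairment term could show.** Start from the plan's SDMT figure of 80% power with 20 per group. It is reproduced with f = 0.19 if rho is about 0.65: lambda = 0.19^2 x 40 x 2 / 0.35 = 8.25, and with df 1 and 38 and alpha 0.05 power is 80%. The exact lambda for 80% is 8.27, so the effect in units of the residual SD of change is sqrt(8.27) x sqrt(2/20) = 0.909.

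Suppose impaired patients have this effect and unimpaired patients have none, the setting most favourable to detecting a difference if neither group is harmed:
- 14 impaired and 6 unimpaired per arm: SE = sqrt(2/14 + 2/6) = 0.690; noncentrality 0.909/0.690 = 1.32; power on 36 df about 25%;
- 10 and 10 per arm: SE = sqrt(2/10 + 2/10) = 0.632; noncentrality 1.44; power about 29%.

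A dichotomised term is therefore exploratory at best.

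**The case against.** **Unimpaired patients may respond, so nothing need be lost.** This stands as far as power goes. Preliminary Study 1 reports gains in healthy young adults (d = 0.96) and again in healthy older adults, and the divided-attention test behind the planning is from healthy adults. A reader might multiply the planned effect sizes by 0.7 and infer that SDMT power falls from 80% to about 50%. The documents do not support that. It needs zero effect in every unimpaired patient, which conflicts with the healthy-adult evidence for divided attention. For SDMT, the planning effect comes from MS patients who are not described as selected for impairment, so it may already average over both kinds of patient. But the same evidence creates the interpretive problem: if unimpaired patients gain, the average effect is not evidence of mitigation alone. Preliminary Study 1 did not assess processing speed, so it does not settle the SDMT question either way.

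**The target is MS in general.** Partly right. Study Design asks about improvement in MS, and the objective is to evaluate potential. A patient above a normative cut may also have declined from a personal baseline, so a reader who infers that such patients have nothing to mitigate goes too far. Open entry also serves Aim 2, which needs variation in severity. Requiring impairment at entry is thus a trade-off against generalisability and Aim 2, and its absence is not in itself an error.

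**Aim 2 already covers heterogeneity.** Only in part. MSFC4 and EDSS are severity measures, but cognition is one quarter of the first, and neither is the baseline of a primary outcome.

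**Conclusion.** The mismatch is real and is one of interpretation and efficiency. The aim and rationale concern impaired cognition, entry does not require it, and the Aim 1 analysis cannot separate mitigation from enhancement. By the Background's own figure, at least 30% of people with MS are unimpaired. That figure does not transfer directly to this clinic, and a reader should not take it as the composition of the 40 enrolled.

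The measurable gain from the remedy is modest: about 5% in the standard error from stratification alone, and roughly 5-12% from continuous adjustment, at assumed pre-post correlations of 0.5 to 0.8. The documents support neither a specific loss of power nor the view that the trial must exclude unimpaired patients. The point does not invalidate the trial, but it should be addressed before the conclusion is worded.

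**What to change.** 1. Keep entry open.
2. Randomise after session 1, stratified by baseline SDMT at a stated cut. State how this combines with age matching; with 40 patients only a few strata are workable.
3. For each primary outcome, add its baseline value as a covariate. As baseline is also a level of Session in the planned ANCOVA, the simplest form models the session 5 value on Group, baseline and age.
4. In Aim 2, add one continuous Group x baseline term per primary outcome, labelled exploratory given the power of about 25-29% for a dichotomised version. Fit it to the session 5 value, since a change score contains the baseline.
5. State the conclusion as applying to MS patients not selected for cognitive impairment.

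**Cost.** SDMT and the divided-attention module are already given at session 1 and stimulation starts at session 2, so no new test or visit is needed. Randomisation must wait until session 1 is scored, the allocation procedure and analysis text need amending, and the claim becomes narrower.

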#### Outcome measures (Sessions 1 and 5).

- **Primary outcome measure: Divided attention (Specific Aim 1).** This (and all) outcome measure(s) will be assessed at baseline (pre-tACS; session 1) and at follow-up (post-tACS; session 5). Divided attention will be measured by a divided attention task module (Table 1). The divided attention module is comprised of 3 tasks: visual perceptual discrimination (single task), visuomotor tracking (single

**Table 1. Divided Attention Task Module**

TASK	DESCRIPTION
Perceptual discrimination	Go/No Go like-paradigm; respond to target stimuli while ignoring distractors
Visuomotor tracking	Navigate a character along a dynamically moving road while avoiding walls and obstacles
Multitasking ability	Perform perceptual discrimination and visuomotor tracking tasks simultaneously

task) and multitasking (dual task; both single tasks simultaneously). Performance during perceptual discrimination will be measured with a metric of discrimination performance (d-prime), which is estimated for each participant by comparing hit rates (correct responses to target signs) and false alarm rates (responses to non-targets) and calculated as  $d' = Z(\text{hits}) - Z(\text{false alarms})$ . D-prime cost (dual task - single

task) from the discrimination task will be used as our measure of divided attention because we have previously observed this metric to improve with tACS during this task ([name] et al., 2019; [name] et al., 2017) (Preliminary Study 1).

- **Primary outcome measure: Information processing speed (Specific Aim 1).**

Information processing speed will be assessed with the Symbol-Digit Modalities Test (SDMT). SDMT is widely used in MS clinical trials to measure speed of information processing (Van Schependom et al., 2014). SDMT requires the participant to substitute geometric symbols for numbers while scanning a response key. Verbal, not written, responses will be recorded. The quantity of correct items will serve as the primary measure of processing speed because we have previously demonstrated that this metric improves with cognitive training in MS patients (Preliminary Study 2). Importantly, we will employ the same cognitive paradigm during tACS as we previously used in Preliminary Studies 1 and 2.

- **Secondary outcome measure: Frontal theta power (Specific Aim 1).** The visual

discrimination task (single and dual task) will be used to assess neuroplastic changes in divided attention. We have previously demonstrated (and replicated) that theta-tACS above PFC is able to enhance divided attention abilities (i.e., dual - single task discrimination performance) in healthy adults (Preliminary Study 1). Importantly, increases in midline frontal theta power is correlated with improvements in divided attention. EEG data will be collected during the divided attention task module with a 64-channel BioSemi ActiveTwo system. Raw data will be segmented into epochs beginning 1000 ms before to 1000 ms post stimulus onset, demeaned/detrended and referenced to the average EEG signal. An independent component analysis will be performed to remove components consistent with topographies for blinks and eye movements. Epochs that exceed a voltage threshold of 80  $\mu$ V will be rejected. EP data will focus on amplitudes and latencies of the P1 and N1 components. For the spectral analysis, a fast fourier transformation will be performed from 4 to 30 Hz. The data will be multiplied by a hanning taper, using a sliding time window. Power changes of oscillatory activity as a function of time will be calculated for theta (4-7Hz), alpha (8-12Hz), and beta (13-30Hz) bands with one power value every 10 ms.

- **Exploratory measures (Specific Aim 1).** Three exploratory measures will be used to

assess whether tACS effects extend beyond our hypothesized changes in divided attention and processing speed. Specifically, during sessions 1 and 5 (pre- and post-tACS) we will assess changes in cortical excitability, fatigue and pain. 1) **Cortical excitability** will be assessed via EPs due to their sensitivity to tACS effects (Jamil et al., 2017). 2) **Fatigue** and 3) **pain** will be assessed because previous studies have shown that tDCS improves pain (Ayache et al., 2016; Mori et al., 2010) and fatigue (Ferrucci et al., 2014; Hanken et al., 2016) in patients with MS. To assess fatigue, the Modified Fatigue Impact Scale (MFIS) will be used, which consists of 21 items from the Fatigue Impact Scale (Fisk et al., 1994;

Kos et al., 2005), a multidimensional scale assessing the perceived impact of fatigue on three subscales (Physical, Cognitive, and Psychosocial) of activities, resulting in a total MFIS score. Pain will be assessed via the Brief Pain Inventory (BPI), a 32-item self-administered questionnaire to measure a pain severity score and a pain interference score (Daut, Cleeland, & Flanery, 1983).

- **Covariates to be included in Regression Analyses (Specific Aim 2).** Regression analysis will be performed to identify predictors of tACS effects on the primary outcome measures: divided attention and processing speed. Three classes of predictors will be assessed: neuroanatomy, cortical excitability, and clinical severity, in addition to those typically accounted for in MS studies: demographic (age, gender, education) and clinical features (MS duration, EDSS). 1) **Neuroanatomy.** Differences in the thickness of the skull, cerebrospinal fluid, subcutaneous fat, as well as gyral pattern, and local tissue heterogeneities (such as atrophy) yield differences in resistivity that will differentially impede current flow to cortex (Opitz, Paulus, Will, Antunes, & Thielscher, 2015; Shahid, Wen, & Ahfock, 2013; Truong, Magerowski, Blackburn, Bikson, & Alonso-Alonso, 2013). The consequence of this anatomical variability can lead to 1.5 to 3-fold differences in the induced electric field in cortex (Datta, Truong, Minhas, Parra, & Bikson, 2012; Russell et al., 2013), contributing to variable tES outcomes. Indeed, we have recently demonstrated that the amount of current that reaches the brain predicts tACS efficacy (Preliminary Study 1). Therefore, to assess the amount of tACS-induced current that reaches the brain, individual MRI data will be used to model the electric field within each patient's brain. Standard modeling software will be used for this task (Huang, Datta, Bikson, & Parra, 2019). As patients' annual clinically-acquired brain MRIs are available in [name] BRIDGE platform (bridge.ucsf.edu), funds are not requested to collect MRI data. The average modeled electric field magnitude within the PFC will be used as a predictor variable for the regression analysis. 2) **Cortical excitability.** Evoked potentials (EPs) from the single task version of the discrimination task will be used to assess cortical excitability as a predictor variable in the regression analysis. In MS, demyelination and axonal loss occur, which not only changes the current flow of tES, but alters cortical excitability as measured by EPs (Caramia et al., 2004). EP abnormalities in MS include morphological changes, delayed latencies, wave cancellation and increased refractory period (Iodice et al., 2016). Importantly, baseline cortical excitability, as measured by EPs, has been shown to be a significant covariate associated with variable effects of tES across individuals (Jamil et al., 2017). 3) **Clinical severity.** In a meta-analysis of non-invasive neurostimulation effects, we have shown that patients with the greatest clinical severity are the ones who benefit most from neurostimulation ([name], Ku, [name], & [name], 2015). Here, we will use the MS Functional Composite 4 (MSFC4) as a metric of clinical severity and assess it as a predictor variable in the regression analysis. The MSFC4 assesses four key MS-related functional domains: ambulation (timed 25 foot walk), upper extremity dexterity (9-

Hole Peg Test), vision (low contrast visual acuity) and cognition (PASAT, a test of information processing speed, flexibility, attention, and working memory (Rosti, Hamalainen, Koivisto, & Hokkanen, 2006; Tombaugh, 2006)).

